### PULSEWATCH INVESTIGATOR STUDY PLAN

contact the participant's treating physician to report the findings and recommend follow-up plans. In the unlikely event of incidental findings during Part I, the PI will be contacted if he is not present.

All recruitment and training will be conducted by trained personnel who are certified according to our study protocols, which include training in procedures for recruitment in the clinical environment. Modeled on the PI's ongoing studies, medical record review protocol uses "gold standard" medical records and requires that each abstractor satisfactorily complete 10 practice cases before certification. We will have ongoing data quality control checks via audited interviews and medical records abstracted in duplicate for 5% random samples. If error rates are too high, we will retrain staff and increase quality control sampling until the rates decline to acceptable levels. We will continue our ongoing quality control measures with dynamic range and consistency checks, missing data surveillance, and error tracking.

All study participant Pulsewatch ECG recordings (both from the 14-day monitor and individual AliveCor ECGs) will be manually reviewed by trained study staff under the direction of the PI. Two readers, blinded to the determination of the automated rhythm analysis, will review ECG data and code sinus rhythm, AF, or other arrhythmias (e.g., premature atrial beats) using standard criteria. In cases where there is disagreement with respect to rhythm, the PI will review the tracing to obtain consensus. ECG data will be reviewed within 3 days by a study cardiologist. If cases of AF are detected on manual review or if a participant calls the study hotline to report a new health concern, the research coordinator will notify the participant's primary healthcare provider, cardiologist or neurologist and assist in arranging a follow-up. Providers will be given the PI's contact information to arrange care or to speak with a cardiologist familiar with the Pulsewatch protocol.

All of the Cardiac Insight patch monitoring data will be de-identified using alpha-numeric study IDs. The ECG data from the cardiac monitor will be uploaded to a secure server (UMMS) and downloaded for interpretation. The ECG data from the cardiac monitor will also be uploaded to the secure UConn server and downloaded in order for UConn to compare their PPG data from the smartwatch to the ECG data from the cardiac monitor. Only [name] and the UMass research staff will have access to the code linking the subjects to study IDs. The study cardiologists will review any arrhythmias on the cardiac monitoring device for accuracy. If any arrhythmias are detected, then [name] will notify the participant's treating clinician.

We will report any issues to the UMMS IRB in accordance with the Investigator Manual and Prompt Reporting Requirements.

We will have independent data safety personnel who will evaluate the process of ECG review and reporting as well as any adverse events related or unrelated to study participation. Please see resource available section.

The PHQ-9 and GAD-7 in the questionnaire are the only instruments that require monitoring and a UMMMC Protocol plan has been submitted with this IRB application. Per our protocol, if study staff detect high PHQ-9 and/or GAD-7 scores, they will suggest that participants discuss their symptoms of depression and/or anxiety with their doctors and/or the trained personnel at the UMMMC Emergency Mental Health [contact]). Study staff will be fully trained to note that the checkbox on the cover page of each questionnaire will remind them to follow the extreme emotional distress protocol when warranted.

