## Part II:

At baseline, participants in the Aim 2 control group (up to n=30) will be given two gold-standard Cardiac Insight Cardea Solo patch monitors. Each patch will run for 7-days to automatically monitor for and capture irregular heartbeat data. This patch goes right over a participant's heart on their skin. This patch will allow participants to go home with a continuous AF monitoring method without the hassle of carrying around a bulky Holter device. Our PI has already worked with similar devices in the past and has built a relationship with the study team to ensure proper care and transmission of the data. Trained study staff will place the patch on the participant at

[figure not shown]
the baseline visit. There is little risk to the participant from this device, which is widely used technology. The major risk with this device is participant discomfort or skin irritation. Participants will be given a number to contact in the event they have discomfort in the 14 days of using the device. Participants will be given a handout with instructions and care tips for the patch (see Device Handout in eIRB). Only certain sections of this handout will be given to participants depending on which arm of the trial they are assigned to. Aim 2 control participants will be asked to remove the first patch at the end of day 7 and replace it with the second provided patch and wear it for the next 7 days. They will be asked to return both patches at their follow-up visit (approximately 14 days). At their study visit, the participants will be asked to complete an exam and questionnaire that includes standardized scales. Aim 2 control participants will be compensated for their time and effort, as outlined above. The device will be read by a study physician blinded to intervention/control status. Abnormal findings on the monitoring patch, in either the intervention or control groups, will result in notification to the participant's treating physician.

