## 14. Provisions to Monitor the Data to Ensure the Safety of Subject\*

Please review the Data Safety Monitoring Plan (DSMP) in the eIRB for a detailed description regarding human subject's protection.

This plan recognizes the nature of Part II of this study as a clinical trial and this Part involves more intensive data safety monitoring, including involvement of an independent monitor, [name]. The plan has been reviewed and approved by the Director of the Quantitative Methods Core, [name], who has extensive expertise in the design and conduct of clinical trials.

As outlined in the DSMP, we will employ an adverse event reporting system (see DSMP Report template in eIRB) that will be reviewed by the PI and the independent data study monitor to ensure safety of all enrolled participants. However, we have provided an overview of our analysis and management plan herein. For any incidental findings, the PI will review the recording of the pulse/ECG data and make a clinical decision; if necessary, the PI then will

Pulsewatch ISP V 1.5 Docket#: H00016067

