### 23. RESOURCES AVAILABLE

The study will be led by investigators with extensive experience working with stroke and AF patients. All neurologists/cardiologists, and research coordinators/staff will ensure that regulatory paperwork, such as consent forms and patient confidentiality, are used appropriately.

All recruitment and training will be conducted by trained personnel who are certified according to our study protocols, which include procedures for recruiting study participants in the clinical environment. Modeled on the PI's ongoing studies, our medical records review protocol uses "gold standard" medical records review methods, and requires each abstractor to satisfactorily complete 10 practice cases before certification. We will have ongoing data quality control checks via audited interviews and medical records abstracted in duplicate for 5% random

samples. If error rates are too high, we will retrain staff and increase quality control sampling until errors decline to an acceptable level. We will continue our ongoing quality control measures with dynamic range and consistency checks, missing data surveillance, and error tracking.

Rhythm diagnoses will be determined based on self-initiated or auto-triggered ECG tracings from the gold-standard Cardiac Insight patch monitor. Two readers, blinded to the determination of the automated rhythm analysis, will review all time-stamped monitor recordings and code sinus rhythm, AF, or other arrhythmias using standard criteria. In cases where there is disagreement between the 2 primary interpreting cardiologists with respect to rhythm, a 3rd physician will review the tracing to obtain consensus.

Personnel Resources are as follows:

- **The PI:** Will be responsible for the direct efforts of the research project and meeting with research coordinators/mangers weekly during the study period. In addition, the PI will adjudicate ECG recordings and, if arrhythmias are detected, will notify the participants' treating clinicians.
- **Co-l's:** Will provide study management, quality assurance, staff oversight, study progress, diagnostic adjudication, data presentation, and preparation of quarterly and annual progress reports. The Co-Is will be available after hours to support research coordinators.

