Determine effects of patient characteristics on Pulsewatch performance	2	90 Pulsewatch users	Area under the curve	Patient characteristics (e.g., sex, hearing or visual impairment)	Chi-square test to compare AUC of 2 independent ROC curves
Examine Pulsewatch usability	3	30 Pulsewatch users	Indicator of watch daily use (yes vs. no) over 1 month	Sex, cognitive function, social support, depression, Barthel)	Mixed effects logistic regression model
Evaluate the impact of Pulsewatch use on key patient-reported outcomes	3	30 Pulsewatch users and 30 controls	Stroke-related quality of life, anxiety & self-activation (Δ from baseline -1 mo)	Potential confounders (e.g. sex, medication adherence and disease-management self-efficacy)	t-test and linear regression model

Aim 2 Analysis: The analysis will focus on examining the performance of Pulsewatch worn for 9 hours daily for 14 days compared to 14-day cardiac monitoring, CardioKey by Biotel. A participant will be classified as having or not having pAF at the end of 14 days based on the gold standard. The total number of positive readings collected over 14 days from Pulsewatch (min 1 pulse every 5 minutes for 504 samples) will be used as the independent variable in a logistic regression to predict the binary outcome of pAF (yes vs. no). The area under the receiver operating characteristic (ROC) curve (AUC) will be calculated based on the results from the logistic regression to evaluate Pulsewatch performance for pAF screening. From the ROC curve, we can identify the cutoff point of total number of positive readings that produces the highest sensitivity and specificity combination. Similar analysis will be conducted using the % of positive readings among all readings collected from each participant as the independent variable. The 95% confidence intervals (CI) of the AUC will be calculated using formula given by Hanley and McNeil. We will then conduct exploratory analyses to examine whether characteristics affect watch performance over 14 days. For example, we will compare the area under 2 independent ROC curves of female vs. male participants (or vision impaired vs. not) using a chi-square test.

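### The reading rule for the Aim 2 reference rhythm is stated inconsistently, and nothing blinds the tie-breaker to the watch data

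*Protocol*

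**What the plan says.** Protocol section 13 (AF Detection Analysis) and the SAP (Aim 2 Analysis) classify each participant as having pAF or not from the reference monitor. That label is the outcome in the logistic regression and ROC analysis. The accounts of how the monitor is read are these:

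- Section 11, Part II: "The device will be read by a study physician blinded to intervention/control status". The patch is described there as continuous and automatic.
- Section 12: the PI receives a summary report of the patch data and reviews it.
- Section 13, Overall Data Management: one cardiologist, called blinded without saying to what, reads the report.
- Section 14: ECG recordings from the 14-day monitor and from AliveCor "will be manually reviewed by trained study staff under the direction of the PI". "Two readers, blinded to the determination of the automated rhythm analysis", code the rhythm. Then: "In cases where there is disagreement with respect to rhythm, the PI will review the tracing to obtain consensus". A later paragraph has study cardiologists check any arrhythmias found on the monitor.
- Section 23: "Rhythm diagnoses will be determined based on self-initiated or auto-triggered ECG tracings from the gold-standard Cardiac Insight patch monitor". Two cardiologists read, and when they disagree a third "physician will review the tracing to obtain consensus". The personnel list in the same section has the PI adjudicate ECG recordings and gives the Co-Is diagnostic adjudication.

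Section 14 also provides, for incidental findings only, that "the PI will review the recording of the pulse/ECG data and make a clinical decision". The SAP gives no reading procedure and names a different monitor, "CardioKey by Biotel", where the protocol has the Cardiac Insight Cardea Solo.

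**The concern.** Sensitivity, specificity and AUC all measure agreement with this one label. An accuracy study needs the label to be set without knowledge of the test under evaluation, by a rule fixed in advance. Here a reader cannot tell which account governs the research classification, and the blinding that is stated does not clearly cover the watch. If the person who settles a disputed tracing has seen the watch data, the label may move towards the watch's answer and the accuracy estimates may be too high. A confidence interval would not reveal this, because it reflects sampling error and not error in the reference. The recording that is read matters too: a reference built only from triggered tracings could miss AF that the watch correctly finds, which would lower apparent specificity.

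**Working it through.** **Step 1. The accounts side by side.**

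| Protocol section | Readers | Tie-break | Blinded to |
|---|---|---|---|
| 11 | one study physician | none | arm |
| 12 | PI, from a summary report | none | not stated |
| 13 | one cardiologist | none | not specified |
| 14 | two readers among trained staff | PI | automated rhythm analysis (readers only) |
| 14, later paragraph | study cardiologists | none | not stated |
| 23 | two cardiologists | third physician | automated rhythm analysis (readers only) |

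The material read also differs: a continuous recording in section 11, triggered tracings in section 23. The sentence after that one in section 23 refers to all time-stamped recordings, so section 23 can itself be read either way.

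**Step 2. Does the stated blinding cover the watch?** Blinding to arm does little here, because all 90 participants in the accuracy analysis are Pulsewatch users (SAP Table 2). Blinding to the automated rhythm analysis may mean the patch software, the watch algorithm or both; the text does not say. In both sections that blinding is attached to the two primary readers. No sentence extends it to the PI in section 14 or to the third physician in section 23.

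**Step 3. Could the tie-breaker have seen watch data?** Under section 14 the PI breaks ties and also reviews pulse/ECG recordings when there is an incidental finding. For those participants the two roles can meet. Patches and watches come back at the same 14-day visit (section 11), and no step locks the rhythm label before watch data become available.

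**Step 4. The plan's own figure.** Inputs from the SAP (Aim 2 Power): n = 90 and 20% pAF, so 18 cases and 72 non-cases; AUC A from .90 to .95. Hanley-McNeil:

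SE² = [A(1−A) + 17(A/(2−A) − A²) + 71(2A²/(1+A) − A²)] / (18 × 72)

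- A = .90: (.0900 + .1391 + 3.0268)/1296 = .002512; SE = .0501; width 2 × 1.96 × .0501 = .197.
- A = .95: (.0475 + .0385 + 1.6430)/1296 = .001334; SE = .0365; width .143.

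The SAP's .14 to .20 reproduces. The point here changes none of these inputs.

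**Step 5. Illustrations under assumption.** No reader-disagreement rate is given, so these show scale and are not estimates.

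- *AUC.* Take AUC = .90, and one case missed by the watch that ranks at chance (.5) among non-cases. Relabelled as no AF, it leaves 17 cases averaging (18 × .90 − .5)/17 = 15.7/17 = .924 against the original 72 non-cases. It also becomes a 73rd non-case, which can only place the result between .924 × 72/73 = .911 and (.924 × 72 + 1)/73 = .925. About .92 is a fair summary.
- *Sensitivity.* With assumed counts of 16 of 18 detected (.889), one such relabelling gives 16/17 = .941.
- *Average effect.* Assume sensitivity and specificity of .9, 20% pAF, a fraction f of participants disputed independently of watch errors, and every dispute settled as the watch called it. Apparent sensitivity is (.18 + .08f)/(.18 + .08f + .02(1−f)): .906 at f = 5% and .925 at f = 20%. Apparent specificity is (.72 + .02f)/(.72 + .02f + .08(1−f)): .905 and .919.

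**The case against.** Several stronger conclusions are tempting, and the documents do not support them.

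- *That the PI routinely sees watch output.* The review in section 14 is limited to incidental findings. Staff upload Aim 2 watch data after the 14-day visit (section 11) to a server managed by UConn (section 12), and UConn compares the watch signal with the ECG (section 14). Nothing says the PI sees watch AF calls before reading a disputed tracing.
- *That readers are not blinded to the watch.* The automated analysis they are blinded to may include the watch algorithm. The scope is unclear; its absence is not established.
- *That the two tie-break rules must conflict.* Section 23 has the PI adjudicate ECG recordings, so its third physician may be the PI. The sections would then agree on the tie-break, but still differ on the readers and the recording.
- *That participant-initiated tracings follow watch alerts.* The self-check prompted by a watch detection uses the wrist electrode (section 13, Smartwatch Data). No text tells participants to trigger the patch after an alert.
- *That the SAP's device name points to bias.* The SAP is dated 11/20/18 and the protocol contains COVID-19 procedures, so the mismatch is probably a version lag.

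It is also fair that a disputed tracing matters only if it decides the participant's 14-day status, and that the one-case AUC shift of .024 is about a quarter of the confidence half-width of .098. What stands is the disagreement over the reading procedure and the missing blinding of the tie-breaker.

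**Conclusion.** The point holds as an internal inconsistency with a possible, unquantified bias. The protocol does not settle who reads the Aim 2 reference, from which recording, or who breaks ties, and no text blinds the tie-breaker to watch data. Followed as written, section 14 allows an unblinded tie-break, and section 23 can be read as allowing a reference based on triggered tracings only.

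The documents do not show that the reference leans towards the watch. An upward shift needs the tie-breaker to have seen the watch data, to be influenced by it, and to decide the participant's status. On average the effect may be small: with up to 20% of participants disputed and every dispute going the watch's way, the gain is at most about .025 in sensitivity and .019 in specificity. With only 18 expected cases, though, a single missed case relabelled as no AF moves sensitivity by about five points (.889 to .941) and AUC from .90 to about .92, under the assumptions shown. The inconsistency should be settled before labels are assigned.

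**What to change.** State one rule, in the same words, in the protocol and the SAP:

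- The reference is the full continuous Cardea Solo recording, read by two readers.
- Ties go to a physician other than the PI, for example a Co-I, or to the PI only if blinded.
- Readers and tie-breaker are blinded to watch pulse data and watch AF output as well as to the patch's automated analysis.
- The research label is locked, with a date, before watch data are linked to it.
- The PI's incidental-finding and safety review continues separately and does not feed into the research label.

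Remove or cross-refer the other descriptions in sections 11, 12, 13, 14 and 23. Reporting the number of participants whose label depended on a tie-break would let readers judge the possible effect. Separately, reconcile the monitor named in the SAP with the one in the protocol.

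The cost is wording plus a lock step in data management. No new staff are needed, because section 23 already gives the Co-Is diagnostic adjudication. Reading time would rise if only triggered tracings had been planned for, which the documents do not make clear.

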## 15. Withdrawal of Subjects without their consent

Participants, including patients, caregivers and providers, will be able to withdraw from the study at any time. Participants will be withdrawn from the proposed study if they are unable or unwilling to wear the smartwatch and are found to meet exclusion criteria. At that point, they will be informed of why they are being removed from the study and given an opportunity to ask questions.

## 16. Risks to Subjects

No more than minimal physical risks will be involved with this study. First, use of a smartphone or smartwatch does not pose any significant health concerns. Use of a single-lead, FDA-approved, commercially available ECG device (AliveCor) does not require placing of electrodes on the human body and does not pose any physical risk. The Cardiac Insight monitor poses no more than minimal risk, but the monitor may cause skin irritation at the site of application. Prior to approaching patients, we will be screening to ensure that the patient does not have any contraindication to be using the Cardiac Insight patch as listed under exclusion criteria (see section 6). This poses no significant risk to participants since this is the standard device used in clinical practice.

Another potential but minimal risk to participants is feeling psychologically uncomfortable disclosing sensitive information (e.g., depressive symptoms) or performing geriatric assessments (e.g., assessments of cognitive function) while answering questions during the interview process at baseline/follow up visits. Depressive symptoms will be collected as part of the interview and there is the possibility that emotional distress or depression will be identified. There is no risk of extreme stress as a result of participants answering these questions. All study staff interacting with participants will be trained to detect when a participant is feeling uncomfortable and will re-iterate that the participant can stop an interview at any time and can refuse to answer any question for any reason.

Another risk to participants will be the possibility of a breach in confidentiality. However, we will try our best to protect participants' confidentiality to minimize the risk (see data safety plan). All participant data will be held behind secured firewalls at UMMS. As noted in Section 12, ECG and pulse data from all smartphones and watches, as well as ECG data from the Cardiac Insight cardiac monitors, will be sent to a secure server managed by UConn's information technology services. The data will not be transmitted with participant name, DOB, or MRN.

Access to databases will be restricted to only authorized personnel. We will utilize all electronic data capture procedures and, therefore, no paper records will be kept long-term. Any paper records (such as medical record information) that are needed for the study will be destroyed immediately following entry into electronic databases. All consent and other forms that are required to be kept will be kept in a locked file cabinet in locked study offices.

